6.5.10 Early Termination Visit

If a subject is discontinued from study treatment early or withdraws from the study, he/she should be assessed approximately 28 days following the last study treatment administration; if the subject is unable to be evaluated approximately 28 days following the last study treatment administration, he/she should be evaluated as soon as practicable (at least by telephone). All assessments scheduled for Day 56 should be performed at the Early Termination Visit.

6.5.11 Unscheduled Visit

Study subjects may be seen at any time in between scheduled study visits at the discretion of the Investigator and any relevant study assessments performed. The date and reason for the unscheduled visit will be recorded as well as the results of the assessments.

6.6 Pregnancy

Subjects will be instructed to notify the Investigator as soon as possible after becoming pregnant or learning of the pregnancy of a partner. If a subject or partner of a subject becomes pregnant during treatment or up to 120 days following the last study drug administration, the Investigator is instructed to notify Trefoil (or designee) within 24 hours of learning of the pregnancy.

If the subject becomes pregnant while receiving investigational product, the investigational product will be permanently discontinued. Protocol-required procedures for study discontinuation and follow-up must be performed on the subject unless contraindicated by pregnancy. Other appropriate pregnancy follow-up procedures should be considered if indicated.

If the partner of a study participant becomes pregnant, the Investigator is instructed to obtain a Pregnant Partner Release Form and collect relevant information regarding the partner and the pregnancy. The Investigator will discuss the risks and concerns of investigational drug exposure to a developing fetus and counsel the subject and/or pregnant partner (or ensure that such counseling is provided).

Pregnancies will be followed through the outcome of the pregnancy. Newborns should be followed for a minimum of 8 weeks. The Investigator will complete a Pregnancy Surveillance Form and report the information regarding the pregnancy, outcome, and status of the newborn, as appropriate.

Trefoil Therapeutics, Inc.

Confidential and Proprietary

7. ASSESSMENT OF EFFICACY

As described above, the primary efficacy endpoint will be endothelial cell count/ density as measures by specular microscopy. Other efficacy assessments include:

- NEI-VFQ-25
- BCVA
- Pentacam examination
- Slit lamp biomicroscopy
- Pachymetry
- IOP

The primacy efficacy timepoint is Day 56. Please refer to Appendix A for the schedule of events.

8. ASSESSMENT OF SAFETY

8.1 Adverse Events

Investigators will collect information related to adverse events (AEs) throughout this clinical trial. The terms and definitions are consistent with *Guidance for Industry and Investigators Safety Reporting Requirements for INDs and BA/BE Studies, FDA 2012.*

- All AEs occurring in all subjects following exposure to study treatment until 30 days after the last study treatment will be reported.
- AEs will be followed until at least the end of the study.
- AEs considered related to the study treatment by the Investigator (SARs) and SAEs will be followed until resolution, return to baseline, or stabilization (if resolution is not expected).

Changes in the subject's medical condition that occur prior to the first exposure to study treatment will be reported as medical history. At each post-treatment visit, subjects will be asked about any possible adverse events in a non-leading manner. An example of a non-leading method of eliciting AE information is "*Have there been any changes in your health since you were here last*?" Subjects should also be asked about the severity and/or persistence of any AEs that were ongoing at the time of their last visit.

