	Use of Xiidra® (lifitegrast ophthalmic solution) within the 30 days prior to Study Day 0 (either eye)
12.	Systemic (nasal, inhaled, oral, parenteral, or topical) or ophthalmic corticosteroid use in the 30 days prior to Study Day 0 unless approved by the Medical Monitor
	Note: Potential subjects on a stable chronic low-dose that is not expected to change in the 3 months following Study Day 0 may be considered for the study after approval by the Medical Monitor
13.	History of significant allergy, hypersensitivity, or intolerance to any drug compound, food, or other substance
14.	Note: This includes all components and excipients of the study drug Women of childbearing potential who are currently pregnant, breast feeding, planning to become pregnant during the study, or not willing to use highly effective birth control measures (e.g., hormonal contraceptives [oral, implanted, transdermal], or mechanical barrier methods [spermicide in conjunction with a barrier such as a condom or diaphragm], or intra-uterine device [IUD]) during the entire course of the
15.	study Current or recent (e.g., the 30 days prior to Study Day 0) participation in any other, interventional clinical research study
16.	An employee of the site that is directly involved in the management, administration, or support of this study or be an immediate family member of the same

Trefoil Therapeutics, Inc.

Confidential and Proprietary

Clinical Study Protocol TTHX-001

Amendment 1.0: September 8, 2020

	Sub-S	Study	Study TTHX-001									
			Screen	Study Day								
		Visit		0		3	7 ±1	14 ±1	21 ±1	28 ±1	56 ±3	90 ± 7
	1	2-4		Pre	ļ	-						
Informed consent	Х		Х									
Demographics	Х		Х									
Medical and ocular history	Х		Х									
Comprehensive ocular examination												
(including slit lamp examination and dilated exam of			OU						SEf		OU	
the lens, fundus and vitreous)												
Urine pregnancy test (WOCBP)				Х							Х	
Laboratory testing (Chem, Heme, UA, & HbA1c)				Х						Х	Х	
NEI-VFQ-25 ^a				Х							Х	
Optional blood sample for genetic testing				Х								
ADA assay					1					Х	Х	
Pre-injection				Х					Х			
PK sampling					1						Х	
Pre-injection				Х					Х			
1.5 hours after injection					Х				Х			
Study Treatment IC Injection (SE)					Х		Х	Х	Х			
Record Concomitant Medications*	Х	Х	Х	Х	Х	Х	Х	Х	Х	Х	Х	Х
Record Adverse Events					Х	Х	Х	Х	Х	Х	Х	Х
Ocular Assessments					1							
Specular microscopy ^b	OU ^{c,d}	OU	OU	OU	!		OU	OU	OU	OU	OU	OU

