(including automated pachymetry)					i							
Pentacam examination				OU	1						OU	
Best corrected visual acuity ^b			OU	SE	!		SE	SE	SE	SE	SE	SE
Slit lamp biomicroscopy			İ	SE	1		SE	SE	SE	SE		SE
Intraocular Pressure (IOP) measurement				SE e	SE e		SE ^e	SE e	SE ^e	SE	SE	SE

OU=both eyes, SE=Study Eye, a Perform prior to any other assessments, b If subject is to be dilated, perform prior to dilation, c 2

timepoints (1 in the early morning and 1 in the late afternoon), may be different days.^d e IOP pre-dose and post-dose at least every 30 minutes until normalized (defined as less than 5 mmHg higher than pre-injection IOP), ^f dilated exam only in subjects with vitreous in the AC at baseline

*Including all ocular medications

LIST OF ABBREVIATIONS

ADA	Anti-Drug Antibody
AE	Adverse Event
BCVA	Best Corrected Visual Acuity
CEC	Corneal Endothelial Cell
CED	Corneal Endothelial Dystrophies
CIARC	Cornea Image Analysis Reading Center
CRF/ eCRF	Case Report Form/ electronic Case Report Form
CRO	Contract Research Organization
DHHS	Department of Health and Human Services
DLT	Dose limiting toxicity
DMEK	Descemet Membrane Endothelial Keratoplasty
DSEK	Descemet Stripping Endothelial Keratoplasty
ECD	Endothelial Cell Density
EDC	Electronic Data Capture
eFGF-1	engineered FGF-1
ETDRS	Early treatment diabetic retinopathy study
FDA	Food and Drug Administration
FECD	Fuchs Endothelial Corneal Dystrophy
FGF	Fibroblast Growth Factor
GAT	Goldmann Applanation Tonometry
GCP	Good Clinical Practice
HED	Human Equivalent Dose
IC	Intracameral
ICF	Informed consent form
ICH	International Conference on Harmonisation
IOP	Intraocular pressure
IRB	Institutional review board
ITT	Intent to Treat
IUD	Intrauterine device
LOCF	Last Observation Carried Forward
MMRM	Mixed Model Repeated Measures
MRSD	Maximum Recommended Starting Dose
NEI-VFQ	National Eye Institute Visual Function Questionnaire
NOAEL	No Observable Adverse Event Level
PAD	Pharmacologically Active Dose
РК	Pharmacokinetic
PP	Per Protocol
SAE	Serious Adverse Event
SAR	Suspected Adverse Reaction
SE	Study Eye
ТМ	Trabecular Meshwork
WOCBP	Women of Childbearing Potential
wtFGF-1	Wild type FGF-1

TABLE OF CONTENTS

Docu	men	t History
Synop	osis.	
List o	f Ab	breviations
1.	Int	roduction12
1.1	C	Corneal Endothelial Dystrophy
1.2	Т	Treatment Options
1.3	F	GF for the Treatment of Corneal Endothelial Dystrophy 12
1.4	Γ	Diurnal Variation in Ocular Function
2.	Bac	ckground Information
2.1	I	nvestigational Product TTHX1114(NM141)13

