6.3 Concomitant Medications and Treatments

6.3.1 Concomitant Medications

Subjects are expected to receive concomitant medications for the management of concurrent medical conditions. Medications taken during the 28 days prior until 28 days following the last study treatment administration will be recorded. Artificial tears are allowed during the study but other ocular medications must be discussed with the masked Medical Monitor.

6.3.2 **Prohibited Medications**

The following medications are prohibited:

Trefoil Therapeutics, Inc.	Clinical Study Protocol TTHX-001
Confidential and Proprietary	Amendment 1.0: September 8, 2020

- Rho-kinase inhibitors (topical or systemic, e.g.; Fasudil, Netarsudil [Rhopressa])
- Systemic or dermatological cytotoxic chemotherapy
- Hypertonic sodium chloride ointment and drops including Muro 128
- Systemic (nasal, inhaled, oral, parenteral, or topical) or ophthalmic corticosteroids **Note:** Inhaled corticosteroids are acceptable as long as the subject is on stable low doses and the dose is not expected to change for the duration of the study
- Cyclosporine ophthalmic emulsion
- Xiidra ® (lifitegrast ophthalmic solution)

Subjects requiring the use of prohibited medications must be discussed with the masked Medical Monitor.

6.3.3 **Pregnancy Testing and Contraception**

Women of child-bearing potential (WOCBP) are defined as a premenopausal female capable of becoming pregnant. Women who are not WOCBP are those who have not had a menstrual cycle for at least 2 years or who have had hysterectomy, bilateral tubal ligation, or bilateral oophorectomy. Sexually active female subjects who are WOCBP must use at least 1 highly-effective method of contraception or at least 2 less effective methods of contraception (including 1 barrier method), starting at least 1 month prior to Day 0, and male subjects who are sexually active with women of childbearing potential must agree to use a double-barrier method of contraception. Per *ICH M3(R2) Non-Clinical Safety Studies for the Conduct of Human Clinical Trials and Marketing Authorization for Pharmaceuticals*, highly-effective methods are defined as "those, alone or in combination, that result in a low failure rate (i.e., less than 1% per year) when used consistently and correctly." FDA-approved contraceptive methods and estimated failure rates are summarized in Table 2.

Method	Failure Rate
Highly-Effective*	
Sterilization surgery for women	Less than 1%

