- Study Treatment IC Injection (SE) ۲
- Record Adverse Events and Concomitant Medication Use •

6.5.5 Day 14 ± 1

- BCVA •
 - Study eye only
 - Between 07:00 AM and 11:00 AM
 - Pre-injection
- Specular Microscopy (including automated pachymetry)
 - Both eyes
 - Pre-injection
- Slit Lamp Biomicroscopy
 - Study eye only
 - Pre-injection
- IOP
 - Study eye only
 - Pre-injection
 - At least every 30 minutes after injection until normalized (within 5 mmHg of pre-injection measurement)
- Study Treatment IC Injection (SE) •
- Record Adverse Events and Concomitant Medication Use •

6.5.6 Day 21 ± 1

- Obtain Sample for ADA •
 - Pre-injection
- Obtain Sample for PK
 - Pre-injection
 - 1.5 hours after injection
- BCVA •
 - Study eye only
 - Between 07:00 AM and 11:00 AM
 - Pre-injection
- Specular Microscopy
 - Both eyes

- Pre-injection
- Slit Lamp Biomicroscopy
 - Study eye only
 - Pre-injection
- IOP
 - Study eye only
 - Pre-injection
 - At least every 30 minutes after injection until normalized (within 5 mmHg of pre-injection measurement)
- Study Treatment IC Injection (SE)
- Record Adverse Events and Concomitant Medication Use

6.5.7 Day 28 ± 1

- Obtain samples for Laboratory Testing (Chemistry, Hematology, Urinalysis, HbA1c)
- Obtain sample for ADA
- BCVA
 - Study eye only
 - Between 07:00 AM and 11:00 AM
- Specular Microscopy (including automated pachymetry)
 - Both eyes
- Slit Lamp Biomicroscopy
 - Study eye only
- IOP
 - Study eye only
- Record Adverse Events and Concomitant Medication Use

6.5.8 Day 56 ± 3

- Urine pregnancy (WOCBP)
- Obtain samples for laboratory testing (Chemistry, Hematology, Urinalysis, HbA1c)
- Obtain sample for ADA
- Obtain sample for PK
- NEI-VFQ-25
- BCVA
 - o Study eye only
 - Between 07:00 AM and 11:00 AM
- Specular Microscopy (including automated pachymetry)

 Both eyes
- Comprehensive Ocular Examination
 - Slit-lamp biomicroscopy
 - Dilated examination of lens, fundus, and vitreous. Note: dilation should be performed after BCVA and measurement of IOP.
 - Both eyes
- IOP
 - Study eye only
- Pentacam examination

- Both eyes
- Record Adverse Events and Concomitant Medication Use

6.5.9 Day 90 ± 7

- BCVA
 - Study eye only
 - Between 07:00 AM and 11:00 AM
- Specular Microscopy (including automated pachymetry)

 Both eyes
- Slit Lamp Biomicroscopy
 - Study eye only
- IOP
 - Study eye only
- Record Adverse Events and Concomitant Medication Use

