Appendix A: Schedule of Events

	cb. c.					Stue	Study TTHX-001	X-001				
	knnie-ane	uuy	Concord					Study Day)ay			
	Visit	it	Screen	0					1 - 10	1001	61.73	E - 00
	1	2-4		Pre		n	TI /	I + I	I # 17	I ⊞ 0 7	CH 0C) I I UY
Informed consent	Х		Х									
Demographics	Х		Х									
Medical and ocular history	Х		Х									
Comprehensive ocular examination												
(including slit lamp examination and dilated exam of the lens, findus and virteous)			OU						SE^{f}		OU	
Trine memanov test (WOCBP)				×							×	
Laboratory testing (Chem. Heme, UA, & HbAlc)				×						Х	×	
NEI-VFQ-25ª				X							Х	
Optional blood sample for genetic testing				Х								
ADA assay										Х	Х	
Pre-injection				×					X			
PK sampling											Х	
Pre-injection				×					X			
1.5 hours after injection					Х				Х			
Study Treatment IC Injection (SE)					Х		Х	Х	Х			
Record Concomitant Medications*	Х	Х	Х	Х	Х	X	X	Х	Х	Х	Х	Х
Record Adverse Events					Х	Х	Х	Х	Х	Х	Х	Х
Ocular Assessments												
Specular microscopy ^b	OU ^{c, d}	OU	NO	ΟŪ			OU	OU	OU	OU	OU	OU
(including automated pachymetry)												
Pentacam examination				OU							OU	
Best corrected visual acuity ^b	OU ^{c, d}		OU	SE			SE	SE	SE	SE	SE	SE
Slit lamp biomicroscopy	OU ^{c, d}			SE			SE	SE	SE	SE		SE
Intraocular Pressure (IOP) measurement	OU ^{c, d}			SE°	SE°		SE°	SE°	SE°	SE	SE	SE
OII=both eves SE=Study Eve ^a Perform mrior to any other assessments ^b If subject is to be dilated nerform mrior to dilation °2 timenoints (1 in the sarly morning and 1 in the late	its ^b If subie	set is to he	dilated nerfor	n nrior to	dilatio	n coti	menoin	s (1 in t	he early	morning	rand lin	the late

OU=both eyes, SE=Study Eye, ^a Perform prior to any other assessments, ^b If subject is to be dilated, perform prior to dilation, ^c 2 timepoints (1 in the early morning and 1 in the late afternoon), may be different days. ^d The OSS AM assessments can be used for screening, ^e IOP pre-dose and post-dose at least every 30 minutes until normalized (defined as less than 5 mmHg higher than pre-injection IOP) ^f dilated exam only in subjects with vitreous in the AC at baseline *Including all ocular medications

Trefoil Therapeutics, Inc. Confidential and Proprietary

This page intentionally left blank

Trefoil Therapeutics, Inc.

Confidential and Proprietary

PROTOCOL SIGNATURE PAGE

TREFOIL DISCLOSURE STATEMENT

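### Sections 8.1 and 6.3.1 end collection of new adverse events and medications at about Day 51 and Day 49, but the Day 90 visit and both schedules still record them

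*Protocol*

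**What the plan says.** Two sentences set a collection period that ends relative to the last dose:

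- Section 8.1, first bullet: "All AEs occurring in all subjects following exposure to study treatment until 30 days after the last study treatment will be reported".
- Section 6.3.1: "Medications taken during the 28 days prior until 28 days following the last study treatment administration will be recorded".

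Other passages run to Day 90 or have no end date:

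- Section 8.1, opening sentence: "Investigators will collect information related to adverse events (AEs) throughout this clinical trial".
- Section 8.1, on visits: "At each post-treatment visit, subjects will be asked about any possible adverse events in a non-leading manner". Asking about the course of events already known is listed there as a further task.
- Section 4.2 has all adverse events recorded whatever their suspected cause, with no end date.
- Section 6.5.9 (Day 90) closes with "Record Adverse Events and Concomitant Medication Use".
- The synopsis schedule and Appendix A mark the rows "Record Adverse Events" and "Record Concomitant Medications" at Day 90. The footnote to the medication row adds "Including all ocular medications".

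Sections 4.4 and 6.5 place the last injection at Day 21 ±1 and the last visit at Day 90 ±7.

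**The concern.** The protocol gives two answers to one question: when does collection of new adverse events and concomitant medications stop? The visible text does not say whether the 30-day and 28-day periods are upper limits or minimums.

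A site that takes sections 8.1 and 6.3.1 as limits would not record a new non-serious event starting after about Day 51, or a medication taken after about Day 49. A site that works from the Day 90 visit list would record both. The same patient history could then give different data at different sites.

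This is the first clinical study of the product (section 2.2.2), and safety is part of the primary objective (section 3). Section 10.1.1 also counts use of an excluded concomitant medication as an important deviation. Under the section 6.3.1 limit, such use after about Day 49 need not reach the database.

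**Working it through.** **Inputs**

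- Last injection: Day 21 ±1, so Day 20 to 22 (sections 4.4 and 6.5.6).
- Adverse event period: last dose + 30 days (section 8.1).
- Medication period: last dose + 28 days (section 6.3.1).
- Last visit: Day 90 ±7, so Day 83 to 97 (section 6.5.9).

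The protocol gives no figure of its own for the gap, so there is none to reproduce.

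**All four injections on schedule**

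Cut-off = last injection + period. Gap = Day 90 visit − cut-off. Share = gap ÷ (Day 90 visit − last injection).

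| | Adverse events | Medications |
|---|---|---|
| Cut-off, nominal | 21 + 30 = Day 51 | 21 + 28 = Day 49 |
| Cut-off, range | Day 50 to 52 | Day 48 to 50 |
| Gap, nominal | 90 − 51 = 39 days | 90 − 49 = 41 days |
| Gap, shortest | 83 − 52 = 31 days | 83 − 50 = 33 days |
| Gap, longest | 97 − 50 = 47 days | 97 − 48 = 49 days |
| Share, nominal | 39/69 = 57% | 41/69 = 59% |
| Share, range | 31/61 = 51% to 47/77 = 61% | 33/61 = 54% to 49/77 = 64% |

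The denominators are 90 − 21 = 69, 83 − 22 = 61 and 97 − 20 = 77 days.

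**Delayed last injection.** Section 4.5.1 allows a 7-day hold. If the held dose is postponed to Day 28 and not skipped (an assumption), the cut-offs move to Day 58 and Day 56. The gaps are then 90 − 58 = 32 and 90 − 56 = 34 days. For the adverse event period to reach even the earliest Day 90 visit, the last injection would have to fall on Day 83 − 30 = 53 or later.

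**Early stoppers.** Section 5.3 expects subjects who stop treatment to stay on study. If they stay to nominal Day 90:

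| Last injection | Adverse event gap | Medication gap |
|---|---|---|
| Day 0 | 90 − 30 = 60 days | 90 − 28 = 62 days |
| Day 7 | 90 − 37 = 53 days | 90 − 35 = 55 days |
| Day 14 | 90 − 44 = 46 days | 90 − 42 = 48 days |

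If the Early Termination Visit (section 6.5.10, about 28 days after the last dose) is their last visit, the gap is about zero.

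**Day 56.** This visit (Day 53 to 59) also falls after both cut-offs on the planned schedule. It is not counted as a contradiction. It is the first visit after Day 28, so it can collect events and medications back to the cut-offs. Section 6.4.11 also requires clinically significant laboratory abnormalities to be reported as adverse events, and that covers the Day 56 samples.

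**The case against.** The strongest reply is that section 8.1 says what will be reported up to 30 days and does not say that later events are excluded. Sections 4.2 and 6.5.9, both schedules and the opening of section 8.1 all point to Day 90, so a careful site would collect to Day 90 anyway. Alternatively, the Day 90 adverse event entry could serve only to follow up known events, since section 8.1 follows events to at least the end of the study.

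The follow-up reading fails. Section 8.1 has subjects asked at every post-treatment visit about any possible event, and separately about ongoing ones. The first question brings out new events, which the 30-day bullet would then leave out. Nor does this reading help with medications: section 6.3.1 states a recording window, and both schedules go past it. Discussing other ocular or prohibited medications with the masked Medical Monitor is a safeguard, but it is not database recording.

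Several limits on the point do stand:

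- The harm depends on a site following sections 8.1 and 6.3.1 over its Day 90 visit list.
- The gaps measure calendar time, not expected lost events.
- Visual acuity, slit lamp, pressure and specular microscopy with pachymetry are still done at Day 90, so late findings in the study eye are captured as examination data.
- The primary endpoint, the change in cell density at Day 56, is not touched.
- The statistical section is not visible in the public copy, so any treatment-emergent definition there cannot be checked.
- Serious events are outside the claim, because section 8.3 requires all of them to be reported. It gives no end date of its own, though, so the reconciled text could usefully state one.

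**Conclusion.** The inconsistency is real and should be fixed. The firm conflict is at Day 90. Read as limits, sections 8.1 and 6.3.1 would leave more than half of the time between the last injection and the Day 90 visit without new non-serious adverse events (nominally 39 of 69 days) and without medications (41 of 69 days). A 7-day dose delay shortens the gaps but does not close them.

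These sizes assume four injections within their visit windows and a site that applies the two sentences strictly. Follow-up of known events and the scheduled examinations are not affected. No difference between arms is claimed. The defect is uneven capture of late safety data across sites.

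**What to change.** Reconcile sections 8.1 and 6.3.1 with section 6.5.9 and both schedules:

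1. State one collection period for new adverse events and one for concomitant medications. Each should run through the Day 90 visit, or the last study visit if earlier, for every subject whatever the number of injections received.
2. State that laboratory abnormalities reportable under section 6.4.11 fall within that period, so that Day 56 results are plainly covered.
3. If 30 days after the last dose is wanted for analysis, keep it as a treatment-emergent flag and not as an end to collection.

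The core change is to two sentences. The Day 90 visit already exists and already lists both items, so no visit or procedure is added. The cost is a few more adverse event and medication records.
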